6.4.3 Other mixed methods studies

These studies will mostly be exploratory, particularly the qualitative studies which seek to understand perceptions, values, attitudes, and beliefs. Process evaluation criteria will be evaluated according to the MRC criteria.³⁵

Service provision assessments, at baseline and each quarter during implementation, will assess: adherence to IMCI (or national guidelines) and device guidelines (only in relevant arms),

including proportion of: caregivers asked about all three danger signs; caregivers asked about all main symptoms; children with cough or difficulty breathing in whom a respiratory rate is counted for a minute and (where applicable) in whom a pulse oximetry reading is attempted, conducted correctly, obtained at first attempt or at repeated attempts; and proportion of children in whom CDSA is used and recommendations are adhered to. Furthermore, correctness of classification and treatment (as far as is possible with available information), and other indices of quality of care will be assessed. Facility and healthcare provider factors associated with health and quality of care impact and intervention uptake will be assessed.

Facility-based process maps and associated non-participant observational data will be described and compared between baseline and early and late intervention periods. Time (in minutes) will be compared (pre, early and late intervention) for total in clinic; in consultation; and on use of devices, and any other relevant single steps of the care process. Comparison will be made using mean (if parametric) or median (if non-parametric).

Qualitative enquiry with healthcare providers and caregivers will primarily focus on service provision, the participant response to the intervention and acceptability of devices, with exploration of change in perceptions, attitudes and behaviour over time. With caregivers, we will also explore experience of care and care-seeking behaviour through IDIs, as well as reasons for lost to follow-up and related perceptions and challenges.

The sub-study of stakeholder perceptions, surveys and project data review will primarily focus on the processes, mechanisms and context (i.e. process evaluation criteria with focus on fidelity, dose, reach, context and adaptation) of implementation including adaptations made.

6.4.4 Cost and cost-effectiveness study

- Full implementation cost of the intervention per focal country (cost to health system as well as direct costs paid by the household to the health system)
- Cost per child screened using pulse oximetry devices and CDSA where applicable, compared to cost per child in routine care.
- Cost per DALY averted attributed to the introduction of pulse oximetry both with and without CDSAs modelled on proportions referred to hospital on day zero or by day 7 or requiring secondary hospitalization by day 28 in each arm and the predicted outcomes in each case, using published literature supplemented where necessary by expert opinion. We will utilize data on any other severe outcomes and also use predictors of severity on children who are admitted to hospital.

6.5 Participant timeline

6.5.1 Pragmatic cluster RCT

The study flowchart is presented in Fig. 5. Research assistants will screen and recruit participants in the waiting area prior to consultation as outlined in Section 10.3. Following informed consent and enrolment, research assistants (RAs) will record participant name,

address and contact details (including personal and alternate contacts) for Day 7 and Day 28 follow-up, basic sociodemographic details, reason for attendance and care-seeking. This will be collected from the caregiver before consultation, except in critical / emergency cases who will be seen immediately by the healthcare provider. The clinical consultation will be conducted by healthcare providers who have been advised to use the devices as described above according to the facility allocation.

After the consultation, the RA will use extract information from the clinical records from the caregiver (child health card and / or referral note), and / or from clinic ledgers or medical records. Information will be extracted and recorded on the final diagnosis, oxygen saturation and results of laboratory investigations (if performed), prescribed medication with dosage, referral or follow-up advice and the usage of the pulse oximeter device and/or CDSA (if applicable). Research assistants will seek clarification from healthcare providers in cases where the diagnosis is not clear from the records.

Caregivers will be offered several options for completing follow-ups at Day 7 and Day 28. Follow-up will be conducted remotely when possible. For caregivers who can provide a phone number at the day of enrolment, Day 7 and Day 28 follow-ups will be conducted by phone. If the initial phone call fails and the phone number is valid, at least three attempts will be made on subsequent three days at different times of the day to try to reach the caregiver. If the phone number is not valid, no other call attempts will be made and alternative follow-up options will be initiated if consented for. Except during the initial phone call, follow-up can be carried out with a caregiver other than the one who gave consent at the day of enrolment if this person is able to provide information about the child. For caregivers who cannot provide a phone number at the day of enrolment, community mechanisms will be relied on to arrange a call with the caregiver through a community focal person, e.g. a community health worker (CHW) or a community leader. To this aim, CHWs and community leaders in the targeted study areas will be asked for their consent to have their phone numbers shared with RAs in order to contact caregivers without a phone for their Day 7 and Day 28 follow-ups. Independently on whether they provided a phone number or not, caregivers will be given the alternative option to consent for in-person Day 7 follow-up that will have to be conducted as soon as possible after all remote attempts failed. In-person Day 7 follow-ups could be conducted either at the caregiver's household or another specified community location.. If Day 7 follow-up has been unsuccessful, Day 28 follow-up will still be attempted. During both Day 7 and Day 28 follow-ups, a structured questionnaire will be administered to assess the primary and secondary outcomes, including details of any government or private hospital admission. In case of non-recovery, if the child is still at home, the study team will advise the family to return to the PHC clinic for a follow-up consultation.

Additionally, visit information from government-designated hospital records will be collected retrospectively for children reported to have attended hospital by the caregiver at follow-up or referred at day 0 and lost to follow-up including clinical assessment on arrival (vital signs, admitting diagnosis), admission details (duration, if oxygen was administered, intensive care

admission) and admission outcome (final diagnosis, discharge against medical advice, death). The same data will be collected for children who visit a non-hospital higher-level of care (emergency or admission unit of a primary or secondary care facility).

It is expected that some participants may present at the same or another health facility enrolled in the study during the follow-up period. These visits and the findings will be recorded on the appropriate scheduled / unscheduled visit eCRFs.

[figure not shown]

Fig. 5. Flowchart of the pragmatic cluster randomised controlled trial. CDSA = Clinical Decision Support Algorithm. CG = Caregiver. HCP = Healthcare provider. OPD = Out-patient department. Arm 1 not applicable in India.

Tab. 4. Schedule of the visits and associated CRFs for the pragmatic cluster RCT. Arm 1 not applicable in India. The different types of data collectors are represented by the following icons:

 Facility-based research assistants

 Research assistant rotating between different referral health facilities

 Healthcare providers

 Call centre-based research assistant

		Health facility baseline visit			Higher level of care visit ^{1,Err r!} Bookmark not defined.			Scheduled ² or unscheduled visit at any study facility			Phone follow-up		
		Time point / window	Day 0		Day 0-7	Day 1 -28			Day 7	Day 28 [28 - 35]			
		Data collection method	Prospective data collection		Review of medical records / registries	Prospective data collection			Phone interviews	Phone interviews			
		Randomization ³	Arm I	Arm II	Arm III				Arm I	Arm II	Arm III		
Events		Forms											
Informed consent			-										
Screening			TIMCI-01										
Identification & contact information	Full identification		TIMCI-02a										
	Contact information		TIMCI-02b										
	Identification and contact information check		TIMCI-02c										
	Referral facility identification		TIMCI-02d										
	Follow-up identification check		TIMCI-02e										
Socio-demographics			TIMCI-03										
Visit info		Care seeking behaviour, transport and costs for visiting health facility reported by caregiver	TIMCI-04a										

	Visit and admission info recorded by referral facility (medical records, registries) ^{Error! Bookmark not defined.}	TIMCI-04b											
	Patient journey reported by caregiver at follow-up	TIMCI-04c											
Clinical presentation & medical history	Clinical presentation and medical history reported by caregiver at baseline	TIMCI-05a											
	Medical history recorded in clinical notes and / or facility registries	TIMCI-05b											
	Chief complaints and medical history recorded in CDSA	TIMCI-05c											
Basic measurements & physical exams	Basic measurements and physical exams recorded in clinical notes and / or facility registries	TIMCI-06a											
	Basic measurements and physical exams recorded in CDSA	TIMCI-06b											
Respiratory rate & pulse oximetry	Respiratory rate and pulse oximetry recorded in clinical notes and/or facility registries ^{Error! Bookmark not defined.}	TIMCI-07a											
	Respiratory rate and pulse oximetry recorded in CDSA ^{Error! Bookmark not defined.}	TIMCI-07b											
	Respiratory rate and oxygen saturation recorded at arrival by referral facility ^{Error! Bookmark not defined.}	TIMCI-07c											
Laboratory investigations	Laboratory investigations recorded in clinical notes	TIMCI-08a											

	and / or facility registries <small>Error! Bookmark not defined.</small>									
	Laboratory investigations recorded in CDSA ¹ <small>Error! Bookmark not defined.</small>	TIMCI-08b								
Diagnosis & care management	Diagnosis and care management in clinical notes and / or facility registries (medical records, discharge summaries)	TIMCI-09a								
	Diagnosis and care management recorded in CDSA	TIMCI-09b								
	Diagnosis and care management recorded by referral facility (medical records, discharge summaries)	TIMCI-09c								
Follow-up at Day 7		TIMCI-10								
Follow-up at Day 28		TIMCI-11								

¹ Data will be collected retrospectively for visits at facilities offering a higher level of care, including district hospitals, any study facility receiving referrals or admitting patients.²
If appropriate for clinical management.

³ Allocation at the level of the facility to intervention or control groups.

6.5.2 Other mixed methods studies

An overview of the timeline for participants recruited to the mixed methods studies and how they are embedded in the pragmatic cluster RCT is shown in Fig. 6. In the sub-sample of children (and their caregivers) selected as part of the SPA, two additional time-points of data collection will occur – during the consultation (observation), and after their clinical consultation (exit interview).

IDIs and FGDs with caregivers, and FGDs will take place after the day 7 follow-up phone call.

[figure not shown]

Fig. 6. Overview of the mixed methods studies and how they are embedded within the pragmatic cluster RCT. CG = Caregiver. HCP = Healthcare provider. Healthcare provider focus group discussions will group healthcare providers from different facilities.

Healthcare providers for the SPA will be invited to participate in the interview and consultation observations at the time of the first SPA assessment at that facility, after information has been provided to and assent obtained from the facility in-charge. At subsequent assessment rounds, the SPA team will meet with the in-charge and HCPs briefly, provide information on updates if required and answer any questions. Prior to participation in the interview or observation, continued consent will be checked verbally by a member of the SPA team. If the supervisor was

not involved in a previous round, they will be fully informed as per the first round, and similarly if an HCP was not previously recruited, the full written informed consent process will be adhered to.

Healthcare providers recruited for qualitative interviews or FGDs will be invited for an interview/FGD from SPA and/or non-SPA facilities. Participants with particularly interesting or divergent views might be approached from FGDs for follow-up IDIs. The final selection of stakeholders (outlined in Section 5.7) will be determined during implementation and based on implementation experience.

6.5.3 Cost and cost-effectiveness study

Facility-based medical and non-medical personnel who provide information for costing will be approached at a time convenient for them so as not to interfere with clinical or health service delivery. Information will be provided about the study and consent will be sought for personal data as outlined in 10.3.3. These providers will be approached pre-intervention and then again during intervention for data collection, though different providers may be approached in case of staff rotation.

6.6 Sample size

The estimated sample sizes for each of the studies are described below, but may be revised during the course of the study. In the case of the RCT, this is due to uncertainty of some of the assumptions (such as eligibility rate and outcome proportions in routine care, for which data reliability is a challenge). Final qualitative sample sizes will be determined based on reaching thematic saturation, i.e. when no new concepts are emerging.

The remaining sample sizes, for SPA, process mapping and time-flow study, have been chosen pragmatically and will vary according to country depending on the degree of difference in care processes between facility types and location, whilst allowing for exploratory analysis into more in-depth aspects of quality of care from baseline to intervention, between the arms, and over time within the intervention period (both due to changes in implementation uptake and seasonal variation in burden of disease).

The sample size for the pilot phase will also be pragmatically based on the degree of difference between facility types and location (and thus the potential need to understand and refine the intervention strategy according to context), but is likely to include between 2 and 4 facilities per arm per country.

6.6.1 Pragmatic cluster RCT

The sample size for the pragmatic RCT is calculated separately for each country, based on the following common assumptions:

- power of 80%

- alpha level of 0.05 per arm
- intracluster correlation coefficient (ICC) of 0.001⁵²
- control arm severe complication of 1.1% (based on comparable data from a previous study in Tanzania)³⁰
- control arm appropriate hospitalisation of 1.5% (based on estimates from facility staff)
- a recruitment period of 12 months

In India, Initial sample size calculation for the three arm trial was based on having the power to detect a 30% or greater decrease in severe complication and 30% or greater increase in appropriate hospitalisation for each arm compared to control with 40 cluster per arm. This assumes average recruitment of 510 children per cluster over the 12 month period, based on available DHIS2 data summaries and estimates from facility staff for 2019 indicating, with an average of 110 per CHC per month and 20 children per PHC, assuming that we recruit facilities with an average ratio CHC : PHC of 1:3. Following the decision, based on the pilot, not to introduce the CDSA, facilities were reallocated to the remaining two arms up to 60 facilities per arm.

In Tanzania, we would have the power to detect a 30% or greater decrease in severe complication and a 30% or greater increase in appropriate hospitalisation for each arm compared to control with 22 clusters per arm. This assumes average recruitment of 1680 children per cluster over the 12 month period, based on available DHIS2 data summaries and estimates from facility staff, with an average of 350 children per health centre per month and 70 children per dispensary per month assuming that we recruit facilities with an average ratio of health center : dispensary of 1:3.

Given the challenges in reliability of routine data in both countries for the assumptions on both expected eligibility rate and outcome proportions in routine care, we will assess these during the pilot phase and over the course of the study and make adjustments to the sample size calculation and recruitment strategy as necessary.

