- Proportion of children prescribed an appropriate antibiotic at Day 0 consultation

Sub-group analyses will include age (under 2 months, 2 – 12 months, 13 – 59 months), sex, and clinical presentation (with cough / difficulty breathing, fever, other). Other exploratory analysis will be conducted of individual and health system factors associated with health and patient-centred outcomes.

Mixed methods sub-studies will mostly be exploratory, to evaluate quality of care outcomes and explore perceptions, values, attitudes and beliefs. Process evaluation criteria will be evaluated according to the Medical Research Council criteria.

Cost and modelled cost-effectiveness will assess:

- Full implementation cost of the intervention per focal country (cost to health system as well as direct costs paid by the household to the health system)
- Cost per child assessed using pulse oximetry devices and CDSA per country; where applicable, compared to cost per child in routine care
- Modelled cost per DALY averted attributed to the introduction of pulse oximetry and CDAs

Sample size

The sample size for the pragmatic cluster RCT is calculated separately for each country to compare each of the intervention arms with the control arm. In order to detect a 30% reduction in the severe complication primary outcome (from 1.1% to 0.77%) with 80% power, we estimate a sample size in each country as follows:

- India – Initial sample size calculation for the three arm trial was 0 facilities per arm, recruiting an average of 510 children over the 12 month period, with an average of 110 per CHC per month and 20 children per PHC, and a facility ratio of CHC : PHC of 1:3, equating to 20,400 children per arm over the study. Following the decision not to introduce the CDSA plus pulse oximetry arm, a decision was made to reallocate facilities to the remaining two arms up to 60 facilities per arm.
- Tanzania – 22 facilities per arm, recruiting an average of 1680 children over the 12 month period, with an average of 350 per health centre per month and 70 per dispensary per month, and an average ratio of health center : dispensary of 1:3, equating to 36,960 children per arm over the study

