8.3.1 Pragmatic cluster RCT

Analyses will follow CONSORT guidelines and intention-to-treat principles, including all participants as randomized. A flowchart will describe the inclusion and follow-up of participants by study arm.

Baseline characteristics will be described by study arm with summary statistics such as median and interquartile range or number and percentage; no formal testing between arms will be performed. Outcomes will be described by arm using summary statistics. The two primary outcomes, the proportion of children with a severe complication and the proportion of children appropriately hospitalized, will be assessed using a random effects logistic regression models with the cluster included as a random effect. Results will be reported with odds ratios, risk differences and 95% confidence intervals (CI). Binary secondary outcomes will be evaluated in the same way. Continuous secondary outcomes will be assessed using random effects linear regression models, reporting adjusted mean differences between arms with 95% CIs.

All models will be adjusted for randomization stratification factors and any baseline variables found to be randomly imbalanced across arms. Assessment for imbalances between baseline variables will be by visual inspection only; there will be no formal testing of baseline characteristics across randomized groups.^{53,54}

For the analysis of the primary endpoints, we will use a hierarchical fallback procedure, which is a closed test procedure using a weighted Bonferroni.^{55,56} This method recycles unspent significant levels to test subsequent hypotheses with a pre-specified hypothesis sequence.⁵⁷ This uses alpha propagation making it more powerful than the Bonferroni method.

The primary outcomes will be evaluated according to hierarchy of importance as follows:

H_1 : There is no difference between the experimental arm and control arm with respect to severe complications by day 7

H_2 : There is no difference between the experimental arm and control arm with respect to hospital admissions within 1 day of the primary consultation

First, we would test the null hypothesis H_{12} which is that neither H_1 nor H_2 are significant. We would reject the null hypothesis of H_{12} if either $p_1 \leq \alpha_1$ or $p_2 \leq \alpha_2$ where α is equally distributed between the endpoints i.e. $\alpha_1 = 0.025$ and $\alpha_2 = 0.025$.

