3.4 Sample Size

The sample size for the pragmatic RCT is calculated separately for each country, based on the following assumptions:

- ξ power of 80%
- ξ alpha level of 0.05 per arm
- ξ intra-cluster correlation coefficient (ICC) of 0.001
- ξ 1.1% severe complications in the control arm
- ξ 1.5% appropriate hospitalisations (within 24 hrs of Day 0 and as a results of referral) in the control arm

In India, initial sample size calculation for the three arm trial was based on having the power to detect a 30% or greater decrease in severe complication and 30% or greater increase in appropriate hospitalisation for each arm compared to control with 40 cluster per arm. This assumes average recruitment of 510 children per cluster over the 12 month period (total 40800), with an average of 110 per CHC per month and 20 children per PHC, assuming an average facility ratio CHC : PHC of 1:3. Following the decision, based on the pilot, not to introduce the CDSA, facilities were reallocated to the remaining two arms up to 60 facilities per arm.

In Tanzania, the study would have the power to detect a 30% or greater decrease in severe complication and a 30% or greater increase in appropriate hospitalisation for each arm compared to control with 22 clusters per arm. This assumes average recruitment of 1680 children per cluster over the 12 month period (total 110880), with an average of 350 children per health centre per month and 70 children per dispensary per month, assuming an average facility ratio health center : dispensary of 1:3.

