4 STATISTICAL PRINCIPLES

4.1 Confidence Intervals and p-Values

For the final analysis of the primary endpoints, a hierarchical fallback procedure will be used, which is a closed test procedure using a weighted Bonferroni [3, 4]. This method recycles unspent significant levels to test subsequent hypotheses with a pre-specified hypothesis sequence [5]. It uses alpha propagation making it more powerful than the Bonferroni method.

The primary outcomes will be evaluated according to hierarchy of importance as follows:

H_1 : There is no difference between the experimental arm and control arm with respect to severe complications by day 7.

H_2 : There is no difference between the experimental arm and control arm with respect to appropriate hospitalisation.

First, the null hypothesis H_{12} , which is that neither H_1 nor H_2 are significant, will be tested. The null hypothesis H_{12} will be rejected if either $p_1 \leq \alpha_1$ or $p_2 \leq \alpha_2$, where α is equally distributed between the endpoints i.e. $\alpha_1=0.025$ and $\alpha_2=0.025$.

Failure to reject the null hypothesis H_{12} we shall conclude the study to be negative as neither of the co-primary outcomes were significant and no further analysis will be performed. If the null hypothesis H_{12} is rejected, then H_1 and H_2 will be tested. If $p_2 \leq \alpha_2$ then we reject H_2 and test H_1 as $p_1 \leq \alpha$. If $p_2 > \alpha_2$ then we do not reject H_2 and test H_1 as $p_1 \leq \alpha_1$.

This procedure will be followed for each of the two experimental arms compared to the control arm. All outcomes will be evaluated regardless of the outcome of the first evaluation. For each intervention arm, the overall trial will be interpreted as positive if either primary outcome is positive compared to control.

Results estimates of primary and secondary outcomes will be presented along with the associated two-sided 95% confidence intervals, for both final analysis and analyses performed for DMC meetings. No adjustments will be made for the interim analysis and any other analysis carried out for the DMC review since they will not be conducted with the purpose of efficacy evaluation.

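### Tanzania's stated 80% power for each primary outcome needs alpha 0.05 and equal-sized facilities; the planned tests and facility mix give about 67% (hospitalisation) and 72% (severe complication)

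*Protocol*

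**What the plan says.** Protocol 6.6.1 and SAP 3.4 list the same assumptions: 80% power, "alpha level of 0.05 per arm", ICC 0.001, and control rates of 1.1% (severe complication) and 1.5% (appropriate hospitalisation). For Tanzania, with 22 facilities per arm averaging 1,680 children a year, they state that "we would have the power to detect a 30% or greater decrease in severe complication and a 30% or greater increase in appropriate hospitalisation". The Protocol Summary presents the target as a "30% reduction in the severe complication primary outcome (from 1.1% to 0.77%) with 80% power".

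The same Tanzanian paragraph gives the sizes behind the average, "with an average of 350 children per health centre per month and 70 children per dispensary per month", with one health centre to three dispensaries.

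The tests are set out in Protocol 8.3.1 and SAP 4.1. Alpha "is equally distributed between the endpoints", 0.025 each. Hospitalisation (H2) is tested at 0.025. Severe complication (H1) is tested at 0.05 if H2 is rejected and at 0.025 otherwise. The nulls are of no difference and the intervals two-sided. For each intervention arm, "the overall trial will be interpreted as positive if either primary outcome is positive compared to control".

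For India, power is given only for the superseded three-arm design of 40 facilities per arm; then "facilities were reallocated to the remaining two arms up to 60 facilities per arm". SAP 3.4 adds: "This assumes average recruitment of 510 children per cluster over the 12 month period (total 40800").

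**The concern.** The sample size section and the testing section use different significance levels. The wording in 6.6.1 can be read as covering the two arm comparisons, but it does not cover the split between outcomes. The calculation also appears to treat every facility as average, although a health centre is expected to recruit five times as many children as a dispensary.

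What is at stake is the reading of a single outcome in Tanzania, the only country testing the CDSA. Protocol 6.4.2 expects the greater effect on hospitalisation, and that is the outcome losing most power. A non-significant result on it would be judged against 80%. The three-month review in Protocol 8.3 and SAP 3.6 also checks the sample size assumptions against this benchmark.

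**Working it through.** **Inputs.** Severe complication 1.1% v 0.77%; hospitalisation 1.5% v 1.95% (30% relative changes); ICC 0.001; 22 facilities per arm; mean size 1,680 (Protocol 6.6.1 and Summary). Alpha levels are from Protocol 8.3.1.

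**1. Reproducing the stated design.** n per arm = (z for alpha + z for power)² × [p1(1−p1) + p2(1−p2)] / (p1−p2)².

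- Severe complication at 0.05: (1.960 + 0.842)² × 0.01852 / 0.0033² = 13,348.
- Hospitalisation at 0.05: 13,138.
- Design effect with equal sizes: 1 + 1,679 × 0.001 = 2.679.
- Facilities needed: 13,348 × 2.679 / 1,680 = 21.3, and 13,138 × 2.679 / 1,680 = 20.9. The plan states 22.
- India by the same route: 1 + 509 × 0.001 = 1.509, giving 39.5 and 38.9. The plan states 40.

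At 22 facilities the effective n is 36,960 / 2.679 = 13,796, so power is 81% (severe complication) and 82% (hospitalisation). This is the plan's figure.

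**2. Planned tests, equal sizes.**

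- H2 at 0.025: 73.5%.
- H1 at a flat 0.025: 72.8%.
- H1 under the sequence, independent statistics: 0.735 × 0.813 + 0.265 × 0.728 = 79.0%.

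At 0.025 throughout, 80% power would need 25.8 (H1) and 25.4 (H2) facilities per arm even with equal sizes.

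**3. Adding the facility mix.** Sizes are 350 × 12 = 4,200 and 70 × 12 = 840. At 1:3 the mean is 1,680 and the CV 0.87. With near-optimal cluster weighting, effective n = k × mean of m / (1 + (m−1) × ICC):

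- 4,200 / 5.199 = 807.8 and 840 / 1.839 = 456.8.
- 22 × (0.25 × 807.8 + 0.75 × 456.8) = 11,980.

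| Tanzania, 22 per arm, ICC 0.001 | H1 severe complication | H2 hospitalisation |
|---|---|---|
| Alpha 0.05, equal sizes (as stated) | 81% | 82% |
| Planned tests, equal sizes | 79% | 74% |
| Planned tests, facility mix | 72% | 67% |

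For H1 under the mix: 0.668 × 0.756 + 0.332 × 0.660 = 0.724. If hospitalisation has no effect, H1 power is about 66%. Nearly all of H1's loss comes from unequal size; H2 loses from both causes.

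**4. Success rule.** At least one outcome: 1 − 0.340 × 0.332 = 0.887 with independent statistics, or about 82% at correlation 0.5.

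**5. Sensitivity to method and ICC.**

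- Standard CV design effect: 1 + (1.75 × 1,680 − 1) × 0.001 = 3.939, effective n 9,383, giving H2 55% and H1 60%.
- Simulation of the random-intercept logistic model (beta-binomial data, 5 or 6 large facilities per arm, adjusted for facility type, 10,000 runs per scenario): H2 70% and H1 76% at nominal Wald p-values. Those p-values reject a true null about 4% of the time at the 0.025 level. With the error held at nominal, power is 63% and 68%.
- ICC 0.0005 with the mix: H2 83%, H1 88%. ICC 0.0015: 55% and 60%.
- For 80% at ICC 0.001 with the mix: 30 facilities per arm for H2, 26 for H1 under the sequence.

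**6. India.** Sizes 110 × 12 = 1,320 and 20 × 12 = 240 at 1:3 give a mean of 510. At 60 per arm, effective n = 60 × (0.25 × 569.2 + 0.75 × 193.7) = 17,255. Power is 83% for each outcome at 0.025, and 88% for H1 under the sequence. H2 reaches 80% only from 56 facilities per arm.

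The total of 40,800 is 2 × 40 × 510. The original design is 3 × 40 × 510 = 61,200 and the current one 2 × 60 × 510 = 61,200. The Tanzanian total in the same SAP section, 110,880, counts all arms (3 × 22 × 1,680).

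**The case against.** The strongest reply is that the trial succeeds on either outcome, and about 89% power for that is ample. This stands, and it limits the point to the reading of single outcomes. But the documents claim 80% for each outcome and give no either-outcome figure.

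Second, the result depends on method and ICC: 55% to 76% across methods at ICC 0.001, and 83% or more at ICC 0.0005. That is true, so 67% and 72% are central values, not exact ones. At the plan's own ICC, however, every method that includes the facility mix and the planned tests falls below 80%.

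Third, the alpha split alone leaves H1 at 79%, close to the claim. That also stands; for H1 the problem is facility size.

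Fourth, the sample size is provisional. The pilot and the three-month review can revise it, and a back-up facility list exists. Those provisions concern recruitment, follow-up and control-group rates; none mentions the alpha split or facility-size variation.

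Finally, 40,800 could be the original requirement for the two retained arms. If so, the SAP should say so, because it does not describe the design now in place. The 61,200 in turn assumes that reallocated facilities keep the average of 510.

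**Conclusion.** The concern holds. The stated 80% per outcome in Tanzania depends on a significance level and equal facility sizes that the plan does not use. On the plan's own inputs, power is about 67% for hospitalisation and 72% for severe complication. These figures assume ICC 0.001, the 1:3 mix, near-optimal weighting and, for severe complication, that both effects are real and the test statistics independent. Either-outcome power is about 89% on the same assumptions, so the design is not invalid; the shortfall affects how a single non-significant outcome can be read. India is adequately powered at the full 60 facilities per arm, but the documents do not show this and the SAP's total is wrong for the current design. This should be corrected.

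**What to change.** In Protocol 6.6.1 and SAP 3.4 (and the matching Summary text):

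- Restate Tanzania's power for each outcome at the alpha actually used and with the planned facility mix, naming the method and showing an ICC range. Report either-outcome power beside it.
- State India's power at the number of facilities actually enrolled, and correct the total from 40,800 to up to 61,200.
- If loss to follow-up scored as non-events is shown, label it as an assumption with a range. The documents give thresholds (90% reachable at Day 7 in the pilot, more than 10% missing as the sensitivity trigger) but no expected loss. For Tanzania at 0.025 with the mix, power is about 65–66% at 2% loss, 64% at 5% and 61–62% at 10%.

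Optionally, and not as an error correction, since the written fallback rule is a valid closed test: replacing it with Holm in Protocol 8.3.1 and SAP 4.1 before unblinded analysis would raise Tanzanian hospitalisation power from 67% to 73% (0.660 × 0.763 + 0.340 × 0.668 = 0.731) at the same family-wise error.

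The cost is revised figures in the sample size sections, less favourable for Tanzania. No extra children or facilities are required. The Holm option is one sentence in each document, but it changes the primary testing rule and would need to be handled as an amendment.
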